### **13.2 Sample Size, Accrual Rate and Study Duration**

Based on data of recent trials with a population of individuals with metastatic breast cancer treated with anti-PD-1/PD-1 agents in monotherapy, and considering that our population will not be previously selected by PD-L1 expression status a true rate of 5% or less would not be of clinical interest. The study will follow a two-stage design in the first stage 14 patients will be enrolled. If in this first stage there is at least 1 patient with objective response (complete or partial response), accrual will continue to the second stage where an additional 16 patients will be

enrolled. If there are at least 4 patients with ORR among the 30 evaluable patients, the regimen will be considered worthy of further study. If the true response rate is 5%, the chance the regimen is declared worthy of further study is less than 5%. If the true response rate is 25%, the chance that the regimen is declared worthy of further study is >90%. The design has been evaluated under departures from the assumption that 100% of the enrollments will be confirmed as hypermutated tumors (>9mut/Mb). The rationale for this evaluation is represented by multiple platforms to identify hypermutated tumors and validation of the hypermutation status after enrollment. We considered power based on exact conditional testing (type I error <0.05), with frequencies of non validated hypermutation status equal to 5%, 10%, 15% or 20% in the enrolled population, and analyses restricted to patients with validated hypermutation status. Under these parameters, restricting continuation to the second stage with OR for one or more patients with validated hypermutation status, power is equal to 0.90, 0.90, 0.88, 0.86.

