### **13.3 Analysis of Primary Endpoint**

The primary endpoint is ORR of the experimental combination, which will be assessed among all patients who initiated protocol therapy. Radiographic response will be assessed using RECIST 1.1 criteria as defined in section 11. Objective response will require confirmatory scans as indicated. The ORR (CR + PR) will be reported with 90% exact confidence intervals. (per RECIST 1.1 criteria; Section 11).

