### 13.6 Reporting and Exclusions

#### 13.6.1 Evaluation of Efficacy

For this Phase II trial, the efficacy evaluable population is a modified intent-to-treat (ITT) population. The modified ITT population consists of all patients who initiate protocol therapy, even if there are major protocol therapy deviations. Patients that do not start protocol therapy will be considered unevaluable and will be replaced.

Subanalyses may then be performed on the basis of a subset of participants, excluding those for whom major protocol deviations have been identified (e.g., early death due to other reasons, early discontinuation of treatment, major protocol violations, etc.). However, these subanalyses may not serve as the basis for drawing conclusions concerning treatment efficacy, and the reasons for excluding participants from the analysis should be clearly

reported. If applicable to the endpoint, the 95% confidence intervals should also be provided.

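### The two-stage rule (at least 1 of 14, then at least 4 of 30) has a 5.7% false-positive rate at a true ORR of 5%, not the stated rate below 5%

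*Combined protocol and SAP*

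**What the plan says.** All the design inputs are in Section 13.2 (Sample Size, Accrual Rate and Study Duration).

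- Null rate: "a true rate of 5% or less would not be of clinical interest".
- Stage 1: "The study will follow a two-stage design in the first stage 14 patients will be enrolled". Accrual continues if at least one of them has a complete or partial response, and 16 more patients are then enrolled.
- Final rule: "If there are at least 4 patients with ORR among the 30 evaluable patients, the regimen will be considered worthy of further study".
- Claimed error rate: "If the true response rate is 5%, the chance the regimen is declared worthy of further study is less than 5" per cent.
- Claimed power: above 90% at a true response rate of 25%.

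The same section reports power for analyses restricted to patients whose hypermutated status is validated, with 5%, 10%, 15% or 20% not validated: "power is equal to 0.90, 0.90, 0.88, 0.86". These rest on an exact conditional test with type I error below 0.05.

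Section 13.3 analyses everyone who started protocol therapy and adds: "The ORR (CR + PR) will be reported with 90% exact confidence intervals". Section 13.6.1 fixes the denominator: "Patients that do not start protocol therapy will be considered unevaluable and will be replaced".

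**The concern.** The claim about the error rate is a strict inequality about a fully specified rule, so it can be checked exactly, and it fails. The claim matters because it is the stated chance of carrying an inactive regimen forward on the primary endpoint, and readers of the trial report are likely to repeat it.

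It also creates a mismatch that readers will notice. If the error rate really were below 5%, a success would be expected to go with a 90% exact interval lying above 5%. At the smallest successful count, 4 of 30, it does not.

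**Working it through.** **Inputs** (Section 13.2): n1 = 14, continue if X1 ≥ 1; n2 = 16; success if X1 + X2 ≥ 4; null rate 5%, alternative 25%. Non-starters are replaced (Sections 13.1 and 13.6.1), so the denominator is 30.

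**Formula.** P(success) = Σ over x = 1 to 14 of P(X1 = x) × P(X2 ≥ 4 − x), with X1 ~ Bin(14, p) and X2 ~ Bin(16, p). From x = 4 upward the second factor is 1.

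**Stated power, p = 0.25: reproduced.**

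| x in stage 1 | P(X1 = x) | P(X2 ≥ 4 − x) | Product |
|---|---|---|---|
| 1 | 0.0832 | 0.8029 | 0.066761 |
| 2 | 0.1802 | 0.9365 | 0.168723 |
| 3 | 0.2402 | 0.9900 | 0.237805 |
| 4 or more | 0.4787 | 1 | 0.478660 |
| Sum | | | **0.9519** |

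**Stated error rate, p = 0.05: not reproduced.**

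| x in stage 1 | P(X1 = x) | P(X2 ≥ 4 − x) | Product |
|---|---|---|---|
| 1 | 0.3593 | 0.0429 | 0.015429 |
| 2 | 0.1229 | 0.1892 | 0.023264 |
| 3 | 0.0259 | 0.5599 | 0.014490 |
| 4 or more | 0.0042 | 1 | 0.004173 |
| Sum | | | **0.0574** |

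A simulation of 4 million trials gave 0.0573 and 0.9519.

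**Early stopping is already counted.** In a single stage, P(at least 4 of 30) = 0.0608. The stage 1 stop removes 0.4877 × 0.0070 = 0.0034, which leaves 0.0574.

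**Where the bound would hold.** Solving P(success) = 0.05 gives a true rate of 4.78%. The plan makes its claim at 5%.

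**Nearby rules.**

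| Rule | Error at 5% | Power at 25% |
|---|---|---|
| ≥1/14, then ≥4/30 (as written) | 5.7% | 95.2% |
| ≥1/14, then ≥5/30 | 1.5% | 89.6% |
| ≥2/14, then ≥4/30 | 4.2% | 88.5% |
| ≥1/14, then ≥4/29 | 5.2% | 94.5% |
| ≥1/14, then ≥4/28 | 4.7% | 93.6% |

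Neither of the two alternatives that keep 14 + 16 patients meets both stated properties. A normal approximation that ignores stage 1 does fall below 5% (0.047 with continuity correction), but it is unsuitable with 30 × 0.05 = 1.5 expected responses.

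**Link to the confidence interval.** The 90% Clopper–Pearson interval, ignoring the interim look, is 4.7% to 28.0% at 4/30 and 6.8% to 31.9% at 5/30. Allowing for the two stages, the one-sided 95% lower bound at 4/30 is 4.78%, still under 5%. The chance of passing stage 1 and ending on exactly 4/30 is 0.0421 at a true rate of 5%, or 0.0421 / 0.0574 = 73% of all false positives. At a true rate of 25% it is 0.0564.

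**Sensitivity powers (inference only).** Assume that the number of validated patients is binomial and that at least one validated responder is needed in stage 1.

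| Not validated | Stated | Exact cut-off, alpha <0.05 | Fixed cut-off of 4 |
|---|---|---|---|
| 5% | 0.90 | 0.902 | 0.936 |
| 10% | 0.90 | 0.905 | 0.916 |
| 15% | 0.88 | 0.888 | 0.891 |
| 20% | 0.86 | 0.859 | 0.860 |

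The exact cut-off fits better, though 0.888 does not round to 0.88. That criterion needs 5 responders when 29 or 30 patients are validated, because 4 of 30 exceeds 5%. This suggests, without proving it, that the sensitivity evaluation used a stricter criterion than the main rule.

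**The case against.** The arithmetic is not in dispute; the objections concern weight and remedy.

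- **Size.** An excess of 0.7 points in a single-arm phase 2 screening rule is modest, and the power claim is met. This stands: it makes the matter a correction to the text and no threat to the design.
- **Which item is wrong?** The section uses 5% as its limit twice, so the cut-off could be the mistake and the error statement the intention. The documents do not settle this. But moving to 5/30 drops power to 89.6% and breaks the other stated property, so a mistyped threshold does not explain the discrepancy.
- **The confidence interval point is the same fact seen from the other side.** Largely true. Nothing in the plan requires the interval to exclude 5%, and Section 13.3 does not say whether it allows for the interim look. It is a consequence for readers, not a second error.
- **Evaluability.** Section 11.1.1 has a narrower definition of evaluable for target disease response (at least one cycle and a re-evaluation). Sections 13.1, 13.3 and 13.6.1 govern the primary analysis and keep everyone who starts therapy, so the denominator remains 30.
- **The sensitivity powers concern a different analysis**, and the match depends on an assumption that the plan does not state. With fixed numbers validated (28, 27, 26, 24) the powers are 0.932, 0.922, 0.905 and 0.867. That is fair; the main conclusion does not use them.

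**Conclusion.** The statement is wrong as written. The rule in Section 13.2 has a type I error of 0.0574 at a true ORR of 5%, against a stated value below 0.05. Its power at 25% is 0.952, which agrees with the plan. The result assumes independent patients with a common response rate, 30 evaluable patients, and the rule applied exactly as printed. The practical effect is confined to the stated error rate and to the reading of a result of exactly 4/30; from 5/30 upward the rule and the 90% interval agree. It should be corrected, but it does not undermine the design.

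**What to change.** In Section 13.2, keep the 14 + 16 design and the threshold of 4/30. Restate the chance of success as about 5.7% at a true rate of 5% and about 95% at a true rate of 25%. Add one sentence saying that exactly 4/30 meets the decision rule although its 90% exact interval (4.7% to 28.0%, not adjusted for the interim look) includes 5%. Listing the critical values behind the four sensitivity powers would help readers, but the correction does not depend on it.

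The cost is wording only, plus a slightly less favourable stated error rate. If the sponsor prefers to hold the error strictly below 5%, the rule has to change and both properties must be restated: 5/30 gives 1.5% and 89.6%, so the claim of more than 90% power would go. A total of 28 patients with at least 4 responders gives 4.7% and 93.6%, but that changes the sample size.

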### **13.3 Analysis of Primary Endpoint**

The primary endpoint is ORR of the experimental combination, which will be assessed among all patients who initiated protocol therapy. Radiographic response will be assessed using RECIST 1.1 criteria as defined in section 11. Objective response will require confirmatory scans as indicated. The ORR (CR + PR) will be reported with 90% exact confidence intervals. (per RECIST 1.1 criteria; Section 11).

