### **13.4 Analysis of Secondary Endpoints**

#### Efficacy Endpoints

All patients who initiated protocol therapy will also be evaluated for ORR according to irRC, and for CBR and PFS, according to RECIST. Clinical benefit is defined as CR, PR or SD  $\geq$  24 weeks according to RECIST 1.1. ORR according to irRC will be reported with 90% exact confidence intervals. CBR will be reported respectively with 95% exact confidence intervals. PFS will be analyzed using Kaplan–Meier product-limit estimates and will be plotted using Kaplan-Meier plots. PFS is defined as the time from study randomization to disease progression according to RECIST 1.1, medical judgment or death due to any cause, whichever occurred first. Patients alive without disease progression are censored at the date of last disease evaluation. The hazard ratio for each time-to-event endpoint will be estimated with 95% confidence intervals derived from the Cox proportional hazard model, but no hypothesis testing will be conducted.

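### The 90% exact interval for the primary ORR makes no stated allowance for the stop at 0/14; read as a single-sample interval, its upper limit is too low at 1 to 3 responders in 30 (minor)

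*Combined protocol and SAP*

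**What the plan says.** Section 13.2 sets out the design: "The study will follow a two-stage design in the first stage 14 patients will be enrolled". The continuation rule follows: "If in this first stage there is at least 1 patient with objective response", then "accrual will continue to the second stage where an additional 16 patients will be" enrolled. The final criterion is a count: "If there are at least 4 patients with ORR among the 30 evaluable patients", the regimen is considered worth pursuing. A true rate of 5% or less is of no clinical interest, and power is quoted at 25%.

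For the analysis, Section 13.3 states: "The ORR (CR + PR) will be reported with 90% exact confidence intervals". It names neither the interval method nor any adjustment for the stopping rule, and no other section does so. Section 13.4 uses the same kind of phrase for other rates: "ORR according to irRC will be reported with 90% exact confidence intervals", and 95% exact intervals for clinical benefit rate and for each toxicity.

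**The concern.** An exact binomial interval keeps its error guarantee only if the data come from the distribution that it assumes. Here some trials end at 0/14, so the count at 30 patients is not Binomial(30, p). Some paths to a low total, those with no response in the first 14, have been removed and reported as 0/14 instead. An interval calculated as if 30 patients had always been planned counts those paths wrongly, and the error falls on the upper limit at low counts.

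That limit is what a reader uses after a weak result to judge which response rates have been ruled out. It is also where the plan's wording gives an odd ordering. One responder in 30 would carry an upper limit of 14.9%, below the 19.3% attached to no responders in 14, although 1/30 is the better outcome under the design.

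**Working it through.** **Inputs (Section 13.2 and 13.3).** Stage 1: 14 patients, stop at 0 responses. Stage 2: 16 more, 30 in total. Success: 4 or more of 30. Reference rates 5% and 25%. Interval level 90%, taken as 5% per tail.

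**Distribution under the design.**
- P(stop at 0/14) = (1−p)^14.
- P(reach 30 with s responders) = [C(30,s) − C(16,s)] p^s (1−p)^(30−s). The subtracted term removes the paths with no stage 1 response. The bracket is 30 − 16 = 14 for s = 1, 435 − 120 = 315 for s = 2 and 4060 − 560 = 3500 for s = 3.

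**The plan's own figures first.** P(4 or more of 30) is 95.2% at p = 25%, which agrees with the stated power above 90%. At p = 5% it is 5.74%, which does not agree with the stated type I error below 5%. That is a separate matter of threshold and error statement. It neither causes nor answers the present point.

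**Two-stage exact limits.** Order the outcomes 0/14, 1/30, 2/30 and so on. The upper limit is the p at which the observed outcome and all lower ones together have probability 5%; the lower limit is the mirror image.
- At 1/30, solve (1−p)^14 + 14p(1−p)^29 = 0.05. At p = 0.1982 the terms are 0.0454 + 0.0046 = 0.0500.
- At 2/30, add 315p²(1−p)^28. At p = 0.2177 the terms are 0.0322 + 0.0025 + 0.0154 = 0.0501.

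| Outcome | Clopper-Pearson 90% | Two-stage exact 90% |
|---|---|---|
| 0/14 | 0–19.3% | 0–19.3% |
| 1/30 | 0.2–14.9% | 0.4–19.8% |
| 2/30 | 1.2–19.5% | 1.4–21.8% |
| 3/30 | 2.8–23.9% | 2.9–24.8% |
| 4/30 | 4.7–28.0% | 4.8–28.4% |
| 5/30 | 6.8–31.9% | 6.9–32.1% |
| 8/30 | 14.0–43.0% | 14.0–43.0% |

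**Error of the single-sample upper limit.** At p = 19.55% the outcomes whose upper limit falls below the truth are 0/14, 1/30 and 2/30. Their probabilities are 4.76% + 0.50% + 2.72% = 7.98%, the maximum over p, against a nominal 5%. Lower-tail error stays below 5% throughout. Two-sided coverage has a minimum of 0.895, at p about 19.3%.

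**How often the affected counts occur.** P(1 to 3 of 30) is 45% at p = 5% (15.8 + 18.7 + 11.0), 43% at 10%, 24% at 15%, 10% at 20% and 3% at 25%.

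**Comparison with the plan's rates.** Both intervals exclude 25% at 0/14 and at 1, 2 and 3 of 30, and both include it at 4/30. Both include 5% at 4/30 and exclude it at 5/30. No count gives a different answer against either rate.

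**Point estimate.** Averaged over all outcomes, with 0 for a stopped trial, the expected raw proportion is 3.70% at p = 5% (bias −1.3 points), 8.78% at 10% (−1.2) and 19.53% at 20% (−0.5). Among trials that reach 30 patients it is 7.2% at p = 5% and 11.4% at 10%, so the bias is then upward. The unbiased two-stage estimate (UMVUE) is C(29,s−1) / [C(30,s) − C(16,s)], which gives 1/14 = 7.1% at 1/30, 9.2% at 2/30, 11.6% at 3/30 and 14.3% at 4/30.

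**The case against.** The strongest reply is that the plan does not say which exact interval it means. An interval built on the two-stage distribution is also exact, and Section 13.2 refers to exact conditional testing within the two-stage framework. A reader might infer that the plan has deliberately chosen to ignore the stopping rule; the text does not say so. This stands as a limit on the claim. The single-sample reading is an inference from the identical wording for clinical benefit rate and toxicity, neither of which has a stopping rule. If the two-stage interval was intended, the same added sentence settles it.

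Second, nothing is decided by the interval. Continuation and success rest on counts, and at any count that passes, the upper limit moves by 0.4 points or less. This also stands. A reader might infer that a wrong go/no-go decision could follow; the rule in Section 13.2 rules that out. A reader might also make much of 2/30, where one interval excludes a 20% ORR and the other does not, but 20% is not a rate that the plan uses as a benchmark.

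Third, the downward bias of the raw proportion holds only on average over stopped and continued trials and reverses given continuation. Replacing it with the UMVUE is a trade-off: mean squared error at p = 5% is 0.0027 for the UMVUE against 0.0021 for the raw proportion, though the order reverses at 10% and above. The documents give no ground for saying that the raw proportion must go.

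Fourth, the irRC response rate has the same interval wording, but the stop is governed by the primary objective response, not by irRC response. The two-stage formula does not carry over to it.

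What survives is the upper limit at 1 to 3 responders. On the natural reading it does not have the error rate that the word exact promises, and those counts are likely if the regimen has little activity.

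**Conclusion.** The point holds, as a minor one. If Section 13.3 means the single-sample interval, the upper limit for the primary ORR is too low by 5.0 points at 1/30, 2.2 at 2/30, 1.0 at 3/30 and 0.4 at 4/30, and by a negligible amount from 5/30. Its one-sided error reaches 8.0% against 5%, at a true ORR of about 19.5%. Overall 90% coverage is essentially kept, so a reader who concluded that the interval under-covers in general would go too far. The go/no-go rule and the comparisons with 5% and 25% stand.

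The conclusion assumes an equal-tailed 90% interval, stagewise ordering of outcomes, exactly 14 and 30 evaluable patients, and strict adherence to the stop at 0/14.

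**What to change.** In Section 13.3, for the RECIST 1.1 ORR only, state: *The ORR will be reported with a 90% exact confidence interval that accounts for the two-stage design (stagewise ordering, e.g. Jung-Kim or Koyama-Chen).* Keep the raw proportion as the point estimate; the UMVUE may be shown beside it as an option. Leave the irRC wording in Section 13.4 outside this change. Fix the method before results are known, because at 1 or 2 responders the choice visibly alters the reported limit.

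The cost is one sentence and a few lines of code, with no extra patients or data and no change to the decision rule. The downside is a wider interval, by up to about 5 points, at 1 or 2 responders.

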### **13.4 Analysis of Secondary Endpoints**

#### Efficacy Endpoints

All patients who initiated protocol therapy will also be evaluated for ORR according to irRC, and for CBR and PFS, according to RECIST. Clinical benefit is defined as CR, PR or SD  $\geq$  24 weeks according to RECIST 1.1. ORR according to irRC will be reported with 90% exact confidence intervals. CBR will be reported respectively with 95% exact confidence intervals. PFS will be analyzed using Kaplan–Meier product-limit estimates and will be plotted using Kaplan-Meier plots. PFS is defined as the time from study randomization to disease progression according to RECIST 1.1, medical judgment or death due to any cause, whichever occurred first. Patients alive without disease progression are censored at the date of last disease evaluation. The hazard ratio for each time-to-event endpoint will be estimated with 95% confidence intervals derived from the Cox proportional hazard model, but no hypothesis testing will be conducted.

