**1.3                      Secondary Objectives**

Safety objectives

1.3.1      To evaluate the safety and tolerability of the combination of nivolumab plus ipilimumab.

Efficacy objectives:

- 1.3.2 To evaluate the objective response rate of the combination according to immune-related response criteria (irRC) [Wolchok *et al.*, 2009]. (Section 11).
- 1.3.3 To evaluate the Clinical Benefit Rate (CR + PR + SD  $\geq$  24 weeks) of the combination according to RECIST 1.1.
- 1.3.4 To evaluate the progression-free survival (PFS) of the combination according to RECIST 1.1.
- 1.3.5 To evaluate the Clinical Benefit Rate (CR + PR + SD  $\geq$  24 weeks) of the combination according to irRC [Wolchok *et al.*, 2009]. (Section 11).
- 1.3.6 To evaluate the progression-free survival (PFS) of the combination according to irRC [Wolchok *et al.*, 2009]. (Section 11)
- 1.3.7 To evaluate the objective response rate of the combination according to RECIST 1.1 in the population with centrally confirmed (via Foundation Medicine panel) hypermutated tumors ( $\geq$  9 mutations/megabase)
- 1.3.8 To evaluate the PFS of the combination according to RECIST 1.1 in the population with centrally confirmed hypermutated tumors ( $\geq$  9 mutations/megabase)
- 1.3.9 To evaluate the overall survival (OS) of the combination.

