#### For Participants with Measurable Disease (i.e., Target Disease)

Target Lesions	Non-Target Lesions	New Lesions	Overall Response	Best Overall Response when Confirmation is Required*
CR	CR	No	CR	4 wks Confirmation**
CR	Non-CR/Non-PD	No	PR	4 wks Confirmation**
CR	Not evaluated	No	PR	
PR	Non-CR/Non-PD/not evaluated	No	PR	
SD	Non-CR/Non-PD/not evaluated	No	SD	
PD	Any	Yes or No	PD	no prior SD, PR or CR
Any	PD***	Yes or No	PD	
Any	Any	Yes	PD	

\* See RECIST 1.1 manuscript for further details on what is evidence of a new lesion.  
 \*\* Only for non-randomized trials with response as primary endpoint.  
 \*\*\* In exceptional circumstances, unequivocal progression in non-target lesions may be accepted as disease progression.

Note: Participants with a global deterioration of health status requiring discontinuation of treatment without objective evidence of disease progression at that time should be reported as “*symptomatic deterioration.*” Every effort should be made to document the objective progression even after discontinuation of treatment.

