#### Secondary endpoints include:

Secondary endpoints include the ORR of the combination according to immune-related response criteria (irRC) [Wolchok *et al.*, 2009] (Section 11), the clinical benefit rate according to RECIST 1.1 and irRC, PFS according to RECIST 1.1 and irRC, the OS, the ORR, PFS and OS of the combination according to RECIST 1.1 in the population with centrally confirmed hypermutated tumors ( $\geq 9$  mutations/megabase); and whether the cut off of  $\geq 14$  mutations/megabase is associated with the efficacy of this investigational therapy, assessed by ORR, PFS and OS.

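### PFS is named as a RECIST 1.1 endpoint, but its definition in Section 13.4 also counts undefined medical judgment as an event

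*Combined protocol and SAP*

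**What the plan says.** Objective 1.3.4 reads "To evaluate the progression-free survival (PFS) of the combination according to RECIST 1.1", and objective 1.3.8 reads "To evaluate the PFS of the combination according to RECIST 1.1 in the population with centrally confirmed hypermutated tumors". The endpoint list in Section 13.1 has "PFS according to RECIST 1.1 and irRC". Exploratory objective 1.4.17 also takes PFS per RECIST 1.1. None of these mentions a judgment-based event.

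Section 13.4 opens its efficacy paragraph in the same way: patients will be evaluated "and for CBR and PFS, according to RECIST". The definition that follows is broader. PFS runs to "disease progression according to RECIST 1.1, medical judgment or death due to any cause, whichever occurred first". The trigger at issue is the first item in "medical judgment or death due to any cause". The censoring rule is "Patients alive without disease progression are censored at the date of last disease evaluation". The section says nothing more about the judgment.

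In Section 11, a note to the best-overall-response table says that a patient who stops treatment because of global decline without objective progression is reported as having symptomatic deterioration. It adds: "Every effort should be made to document the objective progression even after discontinuation of treatment".

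**The concern.** The objectives and the analysis section describe different endpoints under one name. An analyst who follows Section 13.4 counts clinical calls that RECIST 1.1 does not recognise as progression. An analyst who follows the objectives does not. Both would label the result PFS by RECIST 1.1.

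The trial is open-label with one arm, so the PFS curve has no internal comparator, and the people making the judgment know the treatment. A reader who sees a RECIST label will take the curve to rest on imaging criteria and deaths. The same patient could also have a PFS event by judgment while response or stable disease is still running under Section 11.1.4, because both durations there depend on the progression criteria.

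**Working it through.** **Comparison of the text.** The plan gives no event count, power or alpha for PFS, so there is no figure to reproduce.

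- Objectives 1.3.4 and 1.3.8, Section 13.1, and the opening of the efficacy paragraph in Section 13.4: PFS by RECIST.
- Definition in Section 13.4: three triggers, namely RECIST 1.1 progression, medical judgment, and death.
- Section 11.1.3.2: the treating physician's opinion carries weight in one case, progression of non-target lesions only, with later confirmation by a review panel or the principal investigator.
- Section 11.1.3.4, note to the table: decline without objective evidence has its own label, and objective progression is still to be sought.
- Section 11.1.4: duration of response ends at objectively documented progression or death.
- Section 5.5: the investigator's judgment that a participant is no longer fit for treatment is a separate reason for stopping, listed apart from RECIST progression.

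Nothing in the documents reconciles the Section 13.4 definition with the rest.

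**Direction.** Let T_R be the time to RECIST progression or death, and T_J the time to a judgment of progression. Section 13.4 takes min(T_R, T_J), which is never greater than T_R. This orders the event times and the underlying curves. Two estimated Kaplan-Meier curves could still cross briefly, because a patient censored at the last scan leaves the risk set before the judgment date.

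**Illustrative size.** Assume constant, independent hazards λ_R and λ_J, and let s = λ_J/(λ_R + λ_J) be the share of first events that are judgment-only. Then:

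- median as defined ÷ RECIST-only median = λ_R/(λ_R + λ_J) = 1 − s
- 24-week PFS as defined = (RECIST-only 24-week PFS)^(1/(1 − s))

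The values of s and the 40% RECIST-only 24-week PFS are assumptions. The documents give neither.

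| s | Median ratio | 24-week PFS if RECIST-only is 40% | Judgment-only events if all 30 patients have an event (30 × s) |
|---|---|---|---|
| 0 | 1.00 | 40% | 0 |
| 5% | 0.95 | 38% | 1.5 |
| 10% | 0.90 | 36% | 3 |
| 20% | 0.80 | 32% | 6 |
| 30% | 0.70 | 27% | 9 |

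For example, at s = 20%, 0.40^(1/0.80) = 0.40^1.25 = 0.318.

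**The case against.** The best defence is that the definition is written out in advance, so a reader of the plan can see what is counted, and that PFS carries little weight. It is secondary, Section 13.4 rules out hypothesis testing, the two-stage rule uses ORR alone, and no external PFS comparison is planned. This stands and limits the consequence. It does not remove the mismatch between label and content.

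A second defence is that the judgment clause may only restate the non-target rule of Section 11.1.3.2. The text does not settle this. Section 13.4 neither cites that rule nor adopts its limits, and progression under that rule is already RECIST progression, so a separate trigger would not be needed.

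A third defence is that dropping judgment events could lengthen PFS through informative censoring. This is a fair point. It is why the judgment-inclusive version should be kept as a sensitivity analysis.

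Several stronger readings are tempting, but the documents do not support them.

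- *A reader might infer that RECIST PFS and irRC PFS are no longer distinct.* They are. RECIST uses unidimensional sums with a 20% and 5 mm threshold and counts new lesions as progression. The irRC rules in Section 11.3 use bidimensional products with a 25% threshold, and new lesions alone are not progression.
- *A reader might infer that treatment beyond RECIST progression lets judgment set the date.* Once RECIST progression occurs, the date is fixed. Judgment matters only before that point.
- *A reader might infer shifts of 6 or 12 weeks, from the gaps between scans.* The calendar footnote on tumor assessments gives scans at C2, C3, C4 and C6, which with 6-week cycles is weeks 6, 12, 18 and 30. Section 11 says about 6-weekly for 24 weeks. Extra scans are allowed when clinically indicated. For a patient never confirmed by imaging, the difference can be event versus censored, which is not a shift in date.
- *A reader might put a count on the patients affected, such as 3 to 6 of 30.* That needs an assumed 10% to 20% share and an event in all 30 patients. The documents supply neither.

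**Conclusion.** The concern holds as a mismatch between label and definition. As written, the curve presented as PFS by RECIST 1.1 is a composite that includes an undefined clinical judgment, and it can only bring a patient's event forward or leave it where it is. The size cannot be known from the documents. The proportional shortening of 5% to 30% depends on the assumed shares and on constant, independent hazards, and the effect is nil if no judgment-only events occur.

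A reader might go further and doubt the trial's main conclusion. The documents do not support that: ORR and the decision to continue or to recommend further study do not use PFS. The point is worth correcting because the rule is wrong for the named objectives and cheap to put right.

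**What to change.** In Section 13.4:

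1. For objectives 1.3.4 and 1.3.8, define the PFS event as RECIST 1.1 progression, including non-target progression under the Section 11 rules, or death from any cause.
2. For patients with clinical deterioration only, use later RECIST progression or death when it is observed, and censor at the last disease evaluation only when neither is. Automatic censoring is not needed: Section 5.6 and the Section 11 note both call for continued assessment after treatment stops.
3. Report the version that also counts progression by medical judgment as a labelled sensitivity analysis. State who makes the judgment and how it is dated.

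Keeping the composite under a new name, with the judgment defined and RECIST-only PFS still reported, would also remove the contradiction.

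The cost is a few sentences and one extra Kaplan-Meier curve. The drawback is possibly informative censoring of patients with clinical progression only. Section 5.6 does not require scans after a new anticancer therapy starts, so some of them will have no RECIST date. The sensitivity analysis shows how much this matters.
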